5.5.2. Estimands for the Other Endpoints

The attributes and strategies for the ICEs that were used for the primary estimand for the primary endpoint analysis (Section 5.3.2.) will also be used for other endpoints (Section 5.5.) except for the endpoints related to extraintestinal manifestations and UC-related hospitalization or surgery,

which will be based on data as observed. The methods to be used to analyze the other endpoints (i.e., binary, continuous, ordinal, and time to event) are defined in the Section 5.5.3. (below).

5.5.3. Analysis Methods for the Estimands for the Other Endpoints

Unless otherwise specified, other efficacy endpoints listed and defined in Section 5.5. above will be analyzed based on **Randomized Full Analysis Set** according to randomized treatment group regardless of the treatment actually received.

All statistical testing will be performed at the 2-sided 0.05 significance level. No adjustments for multiple comparisons will be made for these other endpoints and nominal p-values will be presented.

Binary Endpoints

The intercurrent events captured for binary endpoints specified in Section 5.3.2. will be applied to each of the above binary endpoints except extraintestinal manifestations. Participants with ICEs in categories 1-4 and 6 will be considered not to have achieved the binary endpoints. For participants experiencing an ICE 5, their observed values (if available) will be used. Note that the application of ICE categories 1-3 overrides that of ICE 5.

Participants with any missing data for an endpoint after application of ICE strategies will be imputed as not achieving the associated binary endpoints. Binary endpoints will be summarized with the number and frequency of participants who achieve the endpoint by treatment group, as well as the associated 95% confidence interval. Treatment comparisons (each guselkumab group versus placebo) will be performed using CMH test stratified by clinical remission status at maintenance baseline and induction dose treatment to compare the proportion of participants achieving the endpoints. In case of rare events, the Fisher's exact test will be used for treatment comparisons.

Continuous Endpoints

The ICEs specified in Section 5.3.2. will be applied to each of the above continuous endpoints, i.e., if a participant has an ICE in categories 1-4 and 6, induction baseline values will be assigned from the point of ICE onward (i.e., no change from baseline). For participants experiencing an ICE 5, their observed values (if available) will be used. Note that the application of ICE categories 1-3 overrides that of ICE 5.

To account for the missing data (after applying the ICE strategies) for continuous endpoints of change from baseline measured at more than one post-baseline visit through Week M-44, a Mixed-Effect Model Repeated Measures (MMRM) will be used, under the assumption of missing at random (MAR), to test the difference between each guselkumab group and placebo. In MMRM, missing data will not be imputed, but rather missing data will be accounted for through correlation of repeated measures in the model. Additionally, if the MMRM normality assumption is in question, an appropriate transformation may be implemented before fitting the MMRM model.

The explanatory variables of the MMRM model will include treatment group, clinical remission status at maintenance baseline (Yes/No), and induction dose treatment (guselkumab 400 mg, guselkumab 200 mg, placebo crossover to guselkumab 200 mg), respective baseline score, and an interaction term of visit with treatment group.

An unstructured covariance matrix for repeated measures within a participant will be used. The F-test will use Kenward-Roger's approximation for degree of freedom. In case of lack of convergence, empirical structured covariances will be used in the following order until convergence is reached: 1) Toeplitz 2) first order Autoregressive Moving Average.

The treatment difference between each guselkumab group and placebo will be estimated by the difference in the least squares means (LSmeans). The 95% 2-sided CI for the differences in LSmeans and p-values will be calculated based on the MMRM.

Endpoints that are measured at only one post-baseline visit through Week M-44 (e.g., the full Mayo score or modified Mayo score) will be compared between each guselkumab group and placebo using an analysis of covariance (ANCOVA) with treatment group, clinical remission status at maintenance baseline (Yes/No), induction dose treatment, and corresponding baseline value as covariates.

For analyses using ANCOVA, unless otherwise specified, multiple imputation (same as defined in Section 5.3.2.2.2.) will be used for missing data (after applying ICE strategies), under the assumption that the data are missing at random. The analysis will impute the missing scores at Week M-44 using the corresponding value at baseline and related component score at pre-Week M-44 visits if applicable, clinical remission status at maintenance baseline, induction dose treatment, and treatment group.

Ordinal Endpoints

The ICEs specified in Section 5.3.2. will be applied to each of the above ordinal endpoints, i.e., if a participant has an ICE in categories 1-4 and 6, induction baseline values will be assigned from the point of ICE onward if applicable. For participants experiencing an ICE 5, their observed values (if available) will be used. Note that the application of an ICE in categories 1-3 overrides that of ICE 5.

For the ordinal endpoints, the treatment comparisons (each guselkumab group versus placebo) will be performed using CMH (Row Mean Scores) stratified by clinical remission status at maintenance baseline and induction dose treatment. Missing data (after applying the ICEs) will not be imputed for ordinal endpoints.

Time to Event Endpoints

The time to first loss of partial Mayo response (not meeting the partial Mayo response criteria) and time to first loss of symptomatic remission (not meeting the symptomatic remission criteria) through Week M-44 will be compared between the treatment groups using the stratified log-rank test with clinical remission status at maintenance baseline and induction treatment as the

stratification factors. The Kaplan-Meier curve by treatment group through Week M-44 will be provided. The time to first loss of partial Mayo response or first loss of symptomatic remission is defined as the number of days elapsed from the date of the Week M-0 study intervention administration to the date of the first loss of partial Mayo response or first loss of symptomatic remission prior to or at Week M-44. Participants with an ICE in categories 1-4 and 6 will be considered as having lost partial Mayo response or symptomatic remission from the point of first ICE onward. Participants who have not lost partial Mayo response or symptomatic remission prior to or at Week M-44 will be censored at the last Mayo subscore assessment at or prior to Week M-44.

The time to the first UC-related hospitalization or surgery through Week M-44 will be compared using the stratified log-rank test with clinical remission status at maintenance baseline and induction treatment as the stratification factors. The Kaplan-Meier curve by treatment group will be provided. The time to the first UC-related hospitalization or surgery is defined as the number of days elapsed from the date of the Week M-0 study intervention administration in this maintenance study to the date of the first hospitalization or surgery prior to or at Week M-44. Participants who are not hospitalized nor had a surgery prior to Week M-44 will be censored at Week M-44, date of last available visit (including the safety follow-up visit), or early termination, whichever happens earlier.

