4.1.3.1. Management of Clinical Flare and Loss of Clinical Response

During the Maintenance Study, participants who meet the following criteria will be considered to be in clinical flare:

- an increase from maintenance baseline in the partial Mayo score (ie, the Mayo score without the endoscopy subscore) of at least 2 points and an absolute partial Mayo score ≥ 4 ;
- OR
- an absolute partial Mayo score ≥ 7 points (Section 8.1.1).

Participants in clinical flare between Week M-4 and Week M-32 (inclusive) will be evaluated for loss of clinical response based on the modified Mayo score that includes the endoscopy subscore assigned by the local endoscopist relative to their induction baseline Mayo score. Loss of clinical response means that a participant no longer satisfies the following definition of clinical response:

- a decrease from induction baseline in the modified Mayo score by $\geq 30\%$ and ≥ 2 points, with either a ≥ 1 -point decrease from baseline in the rectal bleeding subscore or a rectal bleeding subscore of 0 or 1.

The management of clinical flare and loss of clinical response during the Maintenance Study is summarized in [Figure 5](#) and described below.

Participants in clinical flare for the first time between Week M-4 and Week M-32 (inclusive) should undergo endoscopy, which need only be a sigmoidoscopy, and be evaluated for loss of clinical response ([Table 2](#) footnote b). These participants should maintain stable doses of their UC medications after meeting clinical flare criteria and while waiting for their endoscopy subscore to establish loss of clinical response. Participants who meet the criteria for loss of clinical response will be eligible for a single blinded dose adjustment as detailed in Section 6.6.1. The dose adjustment can only start between Weeks M-8 and M-32.

[figure not shown]
Participants are strongly encouraged to undergo endoscopy at the time of first clinical flare to establish if loss of clinical response criteria were met. A participant who declines to undergo an endoscopy on initial clinical flare of UC will be discontinued from study intervention administration and should return for a final safety visit approximately 12 weeks after their last dose of study intervention.

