- Change from maintenance baseline in the full Mayo score at Week M-44.
- Change from induction baseline in absolute stool number at each visit through Week M-44.

- Statistical Analysis Plan CNTO1959UCO3001 Amendment 2
- Change from maintenance baseline in absolute stool number at each visit through Week M-44.
- Absolute stool number ≤ 3 at each visit through Week M-44.
- Rectal bleeding subscore of 0 at each visit through Week M-44.
- Stool frequency subscore of 0 or 1 at each visit through Week M-44.
- Change from induction baseline in the endoscopy subscore at Week M-0 and Week M-44.
- Change from maintenance baseline in the endoscopy subscore at Week M-44.
- Ulcerative Colitis Endoscopic Index of Severity (UCEIS) score ≤ 4 at Week M-44.
- Change from induction baseline in the UCEIS score at Week M-44.
- Change from maintenance baseline in UCEIS score at Week M-44.
- Extraintestinal manifestations over time through Week M-44 (i.e., arthritis/arthralgia, aphthous stomatitis, erythema nodosum, iritis/uveitis, pyoderma gangrenosum, and primary sclerosing cholangitis). The attributes and strategies for the ICEs will not be used for this endpoint. Analyses will include the following:
 - Presence of extraintestinal manifestations at maintenance baseline and Week M-44
 - Change from induction and maintenance baseline in arthritis/arthralgia pain level at Week M-44
 - Absence of extraintestinal manifestations among participants with extraintestinal manifestations at induction baseline and maintenance baseline
- Association of histologic-endoscopic mucosal healing, histologic healing, or endoscopic healing at Week M-0 with the following efficacy parameters at Week M-44 will be presented:
 - Clinical remission
 - Corticosteroid-free clinical remission
 - Symptomatic remission
 - IBDQ remission
 - Fatigue response
 - Mayo score
 - Partial mayo score
 - Modified mayo score
 - Stool frequency subscore
 - Rectal bleeding subscore
 - CRP and
 - Fecal calprotectin
 - Clinical flare

- Statistical Analysis Plan CNTO1959UCO3001 Amendment 2
- Clinical remission at Week M-44 and not receiving corticosteroids for at least 12 weeks prior to Week M-44.
- Clinical remission at Week M-44 and not receiving corticosteroids for at least 4 weeks prior to Week M-44.
- Clinical remission at Week M-44 and not receiving corticosteroids for at least 8 weeks prior to Week M-44 among the participants who were receiving concomitant corticosteroids at maintenance baseline.

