- Change from maintenance baseline in PROMIS Fatigue Short Form 7a raw score through Week M-44.
- Change from induction baseline in PROMIS-29 Fatigue Domain raw score through Week M-44.
- Change from maintenance baseline in PROMIS-29 Fatigue Domain raw score through Week M-44.
- $A \ge 5$ -point, ≥ 7 -point, or ≥ 9 -point improvement from induction baseline in PROMIS Fatigue Short Form 5a T-score through Week M-44.
- Change from maintenance baseline in each of the 7 individual raw score items of the PROMIS Fatigue Short Form 7a.
- Participants in fatigue response at Week M-44 among participants with PROMIS Fatigue Short Form 7a T-score ≥ 36.9 at induction baseline.
- Maintenance of fatigue response through Week M-44 among participants in fatigue response at maintenance baseline.

Health Economics

For the endpoints listed below, analysis will be based on the data as observed and the attributes and strategies for the ICEs will only be applied to Work Productivity and Activity Impairment Questionnaire-General Health (WPAI-GH) endpoints:

• UC-related emergency department visits through Week M-44.

- Statistical Analysis Plan CNTO1959UCO3001 Amendment 2
- UC-related hospitalizations through Week M-44.
- UC-related surgeries through Week M-44.
- UC-related hospitalizations or surgeries through Week M-44.
- The time to the first UC-related hospitalization through Week M-44.
- The time to the first UC-related surgery through Week M-44.
- The time to the first UC-related hospitalization or surgery through Week M-44.
- Change from induction baseline in WPAI-GH through Week M-44.
- Change from maintenance baseline in WPAI-GH through Week M-44.

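### The binary-endpoint rule in SAP 5.5.3 codes clinical flare as absent when the flare led to dose adjustment or to stopping for lack of efficacy

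*SAP*

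**What the plan says.** The ICEs are numbered in SAP 5.3.2: ostomy or colectomy (1), dose adjustment including sham (2), prohibited change in UC medication (3), stopping for lack of efficacy or worsening UC (4), stopping for major disruption (5), and stopping for other reasons (6).

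For the other endpoints, the Binary Endpoints paragraph of SAP 5.5.3 says the ICE handling "will be applied to each of the above binary endpoints except extraintestinal manifestations". It then states the rule: "Participants with ICEs in categories 1-4 and 6 will be considered not to have achieved the binary endpoints". Data still missing after that step are also scored as not achieving the endpoint.

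Clinical flare is defined in SAP 5.5.1 from the partial Mayo score. It is used once, as the last item of an analysis in SAP 5.5: "Association of histologic-endoscopic mucosal healing, histologic healing, or endoscopic healing at Week M-0 with the following efficacy parameters at Week M-44 will be presented".

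Two other places set exemptions. SAP 5.5.2 applies the primary-estimand strategies "except for the endpoints related to extraintestinal manifestations and UC-related hospitalization or surgery". The Health Economics lead-in of SAP 5.5, whose list includes "UC-related emergency department visits through Week M-44", says "analysis will be based on the data as observed and the attributes and strategies for the ICEs will only be applied to" the WPAI-GH endpoints. Neither mentions flare.

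Protocol 4.1.3.1 links flare to dose adjustment: "Participants in clinical flare between Week M-4 and Week M-32 (inclusive) will be evaluated for loss of clinical response". Confirmed loss of response then makes the participant eligible for the single blinded dose adjustment.

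**The concern.** The rule has no direction. For remission, healing or response, scoring an ICE as not achieved assigns the bad outcome, as a composite strategy intends. For flare, the same words assign the good outcome.

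The ICEs concerned are often consequences of the flare itself. The planned analysis asks whether healing at Week M-0 goes with less flare later. If flares that had consequences are recoded as no flare, a real association is diluted. A programmer who follows SAP 5.5.3 to the letter would produce that result.

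**Working it through.** The plan states no figure for this point, so there is nothing to reproduce. The check sets the sections side by side and then illustrates the size.

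**Reading the sections together**

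1. Scope. SAP 5.5.3 exempts only extraintestinal manifestations. SAP 5.5.2 adds hospitalization and surgery, and the Health Economics lead-in adds ED visits. Flare is in none of the three, so the rule applies to it as written.
2. From flare to ICE. Under Protocol 4.1.3.1 a first flare from Week M-4 to M-32 leads to endoscopy and evaluation for loss of response, and loss of response leads to dose adjustment. SAP 5.3.1.1 likewise places confirmation of loss of response after a flare. ICE 2 therefore follows a flare, and because sham adjustment counts, this holds in all three arms. A participant who declines endoscopy at the first flare, or who has no partial Mayo response 12 weeks after loss of response, is discontinued from study intervention.
3. Result of the rule. Flare, then ICE 2 or 4, then not achieved, gives no flare. Missing flare data also become no flare.
4. Comparison with the rest of the SAP:
   - SAP 5.3.2 notes that ICEs 1-4 and 6 are an unfavourable outcome.
   - The Time to Event part of SAP 5.5.3 treats the same ICEs as loss of partial Mayo response or of symptomatic remission, that is, as the bad event.
   - The Continuous Endpoints part of SAP 5.5.3 assigns induction baseline values from the ICE onward. In the same association list, a dose-adjusted participant would thus have the partial Mayo score reset to its pre-treatment level while flare is coded absent.

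**Illustration (all rates assumed)**

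Coded flare rate = true rate × (1 − s), where s is the share of flares followed by ICE 1-4 or 6. Take true flare rates of 20% in participants healed at Week M-0 and 40% in those not healed, a difference of 20 points.

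- s = 0.6 in both groups: 20% × 0.4 = 8% and 40% × 0.4 = 16%; difference 8 points.
- s = 0.8 in both groups: 20% × 0.2 = 4% and 40% × 0.2 = 8%; difference 4 points.
- s = 1.0 in both groups: 0% and 0%; difference 0 (a limiting case).
- s = 0.6 in healed and 0.8 in non-healed: 20% × 0.4 = 8% and 40% × 0.2 = 8%; difference 0.

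With equal shares below 1 the ratio stays at 2.0 and only the absolute difference shrinks. With a larger share in the non-healed group the ratio is distorted too.

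**The case against.** The best defence is that the intended direction can be inferred. SAP 5.5 says ICEs enter the variable definitions as appropriate, SAP 5.3.2 calls them unfavourable, and the time-to-event rule counts them as the bad event. The binary paragraph describes between-arm CMH comparisons, whereas SAP 5.1 gives associations between categorical variables a chi-square test. Flare is one item in an exploratory list with nominal p-values. All of this is true and limits the importance of the point. It does not supply a flare derivation: no section states one, and the explicit sentence points the wrong way.

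The illustration is also open to attack. Its rates are not from the documents, and s = 1.0 is not realistic. A flare without loss of response brings no dose adjustment, and Protocol 6.6.1 makes Week M-32 the last visit for one, so later flares cannot produce ICE 2. That criticism stands; the figures show direction and mechanism only.

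A reader might infer three stronger conclusions that the documents do not support:

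- *That UC-related ED visits, hospitalizations or surgeries are erased, for example a colectomy scored as no surgery.* The Health Economics lead-in is specific: these are analysed as observed and "strategies for the ICEs will only be applied to Work Productivity and Activity Impairment Questionnaire-General Health (WPAI-GH) endpoints". SAP 5.5.2 repeats the exemption for hospitalization and surgery. Only a wording mismatch remains: SAP 5.5.2 omits ED visits, and the binary paragraph of SAP 5.5.3 omits all three.
- *That dose-adjusted participants are counted as never having flared.* SAP 5.5 places flare among parameters at Week M-44 and gives no window. If flare status at that visit is meant, someone who flared earlier and then recovered would be a non-flarer on observed data as well. The miscoding would then affect only participants with an ICE who are in flare at Week M-44.
- *That a between-arm comparison of flare is distorted.* SAP 5.5 lists no separate flare endpoint.

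**Conclusion.** The point holds for clinical flare and only for clinical flare. Read as written, SAP 5.5.3 codes a flare that led to dose adjustment or to stopping for lack of efficacy as no flare, against the SAP's own view of what these ICEs mean. The association of Week M-0 healing with flare is weakened. It may also be distorted if the share of flares followed by an ICE differs between healed and non-healed participants.

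The size cannot be derived from the documents; the illustrated drop from 20 points to 8 or 4 rests on assumed flare rates, assumed shares and a cumulative reading of flare. The conclusion about direction needs only that SAP 5.5.3 is applied literally. No confirmatory result depends on it, so this is a small but definite correction.

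**What to change.** In SAP 5.5.3 (Binary Endpoints), limit both the not-achieved rule and the nonresponder imputation to favourable endpoints.

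For the association analysis in SAP 5.5, define flare as flare criteria met at any visit after Week M-0 through Week M-44. Analyse it on data as observed without ICE recoding, so that a flare that precedes a dose adjustment counts as a flare. Use the available visits and do not impute missing as no flare.

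Counting every ICE as a flare is not a good alternative. ICE 6 includes participants who stopped for reasons unrelated to efficacy, and they would be misclassified the other way.

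As a wording alignment only, repeat in SAP 5.5.2 and 5.5.3 the as-observed exemption for UC-related ED visits, hospitalizations and surgeries that the Health Economics lead-in already gives.

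Cost: a few sentences of SAP text and one changed exploratory derivation; no new data.
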